4.3 Exploratory

- 4.3.1 To assess the proportion of women in the FAST-BWL arm who maintain \geq 5% weight loss at 6 months.
- 4.3.2 To describe baseline characteristics (cardiometabolic and obesity biomarkers, microbiome composition, PROs, demographics) of FAST-BWL vs SLOW-BWL, as well as participants who achieve ≥5% weight loss at 6 months vs those who are unable to.
- 4.3.3 To assess prevalence of AA genotype of MnSOD in breast cancer survivors with excess weight and if a greater proportion of women with the AA genotype achieve ≥5% weight loss and improvement in biomarkers at 6 months compared to the women who do not.
- 4.3.4 To determine if women who display the AA genotype of MnSOD and undergo addition of Contrave to BWL have greater weight loss compared to women who do not receive Contrave.

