3. HYPOTHESIS

- In SLOW-BWL, adding Contrave at week 9 of a weight loss intervention may augment BWL and allow women to lose \geq 5% of their baseline body weight at 6 months.
- In SLOW-BWL, weight loss of $\geq 5\%$ baseline body weight will be associated with changes in the following from baseline to 2 and 6 months:
 - o reductions in fasting glucose, fasting insulin, total and low-density lipoprotein (LDL) cholesterol, triglycerides, leptin;
 - o increases in high-density lipoprotein (HDL) cholesterol and adiponectin;
 - o altered gut microbiome (decrease in the ratio of bacteroides and firmacutes); and
 - o improved patient reported outcomes (PROs)
 - o increased total lean mass, and decreased % fat mass and visceral fat
- Compared to women who are able to achieve at least 5% weight loss with 2 months of behavioral intervention alone, women who are unable to achieve ≥5% weight loss with behavioral intervention alone may have identifiable baseline characteristics (i.e., cardiometabolic profile, obesity biomarker, microbiome composition or PROs) that may be predictors of whom may benefit from earlier initiation of pharmacotherapy.

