13. DATA ANALYSIS AND STATISTICAL CONSIDERATIONS

13.1 Study Design

This is a prospective, non-randomized clinical trial assessing the effects of the addition of pharmacotherapy to a behavioral weight loss intervention in overweight/obese breast cancer patients on an AI who are unable to attain at least 5% weight loss after 8 weeks of lifestyle intervention alone.

All enrolled patients will participate in a 6-month BWL program. At week 9, patients who achieve ≥5% weight loss from baseline will continue with BWL (FAST-BWL). Those failing to achieve a minimum of 5% weight loss will receive Contrave in addition to BWL (SLOW-BWL). After a 4-week titration of Contrave, SLOW-BWL will have their drug adherence logs and any new symptoms reviewed by the Protocol Chair and/or co-investigators. The participants will be prescribed the constant dose for 3 months until the end of study (drug will be shipped to patient's home).

The primary endpoint of this study is the proportion of SLOW-BWL patients who achieve at least 5% weight loss of their enrollment baseline weight at 6 months with the addition of Contrave to BWL. We anticipate 55% of 55 subjects enrolled will be in the SLOW-BWL group, resulting in a sample size of approximately 30 SLOW-BWL women and 25 FAST-BWL women.

The secondary endpoints include baseline, 2 and 6 months values in all participants for the following: cardiometabolic biomarkers (fasting glucose, fasting lipids, fasting insulin, adiponectin and leptin levels), genotypes, microbiome composition, body composition, patient-reported outcomes (PROs), and physical activities.

Simon's two-stage minimax design will be used for the SLOW-BWL group. The null hypothesis that the true rate of attaining $\geq 5\%$ weight loss is 10.9%, which is chosen based on the rate of

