women attaining \geq 5% weight loss in the self-directed arm in the POWER-remote study.⁴ In the first stage, 15 SLOW-BWL women will be accrued. If there is 1 or fewer woman out of the 15 women who attain \geq 5% weight loss of their baseline weight, the study will be stopped. Otherwise, 15 additional SLOW-BWL women will be accrued for a total of 30 SLOW-BWL patients. The study does not plan to hold enrollment or treatment for the interim analysis. The null hypothesis will be rejected if 7 or more women are observed in the 30 patients who attain \geq 5% weight loss. This design yields a power of 80% at type I error rate of 5% when the true rate of attaining \geq 5% weight loss of the baseline weight for the SLOW-BWL women is 29%, a clinical meaningful rate for the SLOW-BWL women group.

Our results will inform us of how to better treat obesity in this vulnerable group of breast cancer patients. It may allow us to develop larger adaptive trials to assess long term breast cancer and non-cancer outcomes of behavioral interventions that incorporate pharmacotherapy. Additionally, our results may shed light on other modulators or obesity, such as biomarkers and the microbiome, laying foundation to future trials investigating additional interventions in breast cancer survivors who struggle with weight loss.

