13.2 Analysis Plans

Data will be summarized using descriptive statistics (continuous data) and/or contingency tables (categorical data) for demographic and baseline characteristics, efficacy measurements at 2 and 6 months, and safety measurements throughout the study.

For the primary analysis, the study will be considered successful if there are 7 or more SLOW-BWL patients who could achieve more than 5% weight loss compared to their baseline weight, which implies that the success rate regarding to >=5% weight loss will be significantly higher than 10.9%.

Univariate analysis will be conducted to compare outcomes at different time points including baseline, 2 months and 6 months, and to compare outcomes from different groups including SLOW-BWL patients who attain ≥5% weight loss or <5% weight loss of their enrollment baseline weight at 6 months and FASE-BWL patients. Wilcoxon rank sum and Wilcoxon sign rank tests will be conducted when appropriate. Student's t-test will also be performed when the outcomes are normally distributed after necessary data transformation. Moreover, mixed effect regression analysis will be conducted to evaluate the longitudinal trend in the outcomes at different time points.

Furthermore, multivariate logistic regression analysis will be conducted to evaluate the effect of the baseline characteristics on attaining \geq 5% weight loss of the baseline weight at 2 months among FAST- and SLOW-BWL patients, and to evaluate the effect of the baseline characteristics and the weight loss at 2 months on attaining \geq 5% weight loss of the baseline weight at 6 months for SLOW-BWL patients.

The primary analysis dataset will be based on the intent-to-treat population. Analysis based on the per-protocol population will also be conducted as exploratory analysis. Missing data will be handled by multiple imputation and sensitivity analysis.

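### The 6-month achiever comparison in exploratory objective 4.3.2 mixes FAST and SLOW women, and Hypothesis 3 reads a split made before any Contrave as pointing to who may benefit from the drug

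*Combined protocol and SAP*

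**What the plan says.** Section 4.3, objective 4.3.2, has two halves. The first is "To describe baseline characteristics (cardiometabolic and obesity biomarkers, microbiome composition, PROs, demographics) of FAST-BWL vs SLOW-BWL". The second adds all women by their 6-month result: "as well as participants who achieve ≥5% weight loss at 6 months vs those who are unable to". The second half is not restricted to one group and not stratified by week-9 group.

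Treatment differs after week 9. Women at 5% loss or more continue the behavioral programme (BWL) alone. For the rest, section 13.1 says: "Those failing to achieve a minimum of 5% weight loss will receive Contrave in addition to BWL (SLOW-BWL").

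Section 3, third bullet (Hypothesis 3 here), says that women who do not reach 5% in two months of BWL may have baseline characteristics "that may be predictors of whom may benefit from earlier initiation of pharmacotherapy".

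Section 13.2 opens its group comparisons with "Univariate analysis will be conducted to compare outcomes at different time points". It then lists SLOW achievers, SLOW non-achievers and FAST women as groups, to be compared by Wilcoxon or t-tests. It does not mention the pooled achiever contrast or say how that contrast would be handled.

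Two planned analyses already look inside SLOW. Secondary objective 4.2.2 compares SLOW achievers with SLOW non-achievers at baseline. The second logistic model in 13.2 covers 6-month success in SLOW women and includes 2-month weight loss.

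**The concern.** FAST women need only keep a loss that they already have. SLOW women must reach it from below 5%, with a drug added. A pooled table of achievers against non-achievers therefore carries part of the week-9 split, and with it a treatment difference. A baseline marker related only to early response to BWL can appear in that table as a marker of 6-month success, and a reader cannot tell which group it comes from.

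Hypothesis 3 raises a separate problem of interpretation. The FAST/SLOW classification is made before anyone takes Contrave. No one starts the drug earlier, and no slow responder is assigned to go without it. A baseline difference between the groups describes response to BWL and carries no information about response to the drug.

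Sections 5.11 and 13.1 present the biomarker and microbiome results as groundwork for later trials, so a mislabelled predictor could be carried forward.

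**Working it through.** **The plan's own figures.** Section 13.1 expects 55% of 55 women to be SLOW: 0.55 × 55 = 30.25, "resulting in a sample size of approximately 30 SLOW-BWL women and 25 FAST-BWL women". The Simon design (15 then 30 women, stop at 1 or fewer, reject at 7 or more) has exact power 0.801 at 29% and type I error 0.038 at 10.9%. This agrees with the stated 80% power and lies within the 5% limit. The 30, the 25 and the 29% can be used as they stand.

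**Input that the plan lacks.** No rate is given for FAST women keeping 5% loss from week 9 to month 6; it is itself exploratory objective 4.3.1. I assume 50% to 95%. Section 5.6 offers two loose guides that do not agree well: 38% at 12 months over 46% at 6 months gives 0.83 (a ratio of two marginal rates), while its closing paragraph says only half maintained. Section 5.5 has 63.8%, but for 10% loss at 12 months in people with diabetes.

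**Who the achievers are.** With FAST maintenance m and SLOW success s, FAST achievers = 25m and SLOW achievers = 30s. The FAST share of achievers is 25m / (25m + 30s). At s = 29%, 30s = 8.7.

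| m | FAST achievers | FAST share of achievers | FAST share of non-achievers | phi with week-9 split |
|---|---|---|---|---|
| 50% | 12.5 | 12.5/21.2 = 59% | 12.5/33.8 = 37% | 0.21 |
| 83% | 20.75 | 20.75/29.45 = 70% | 4.25/25.55 = 17% | 0.54 |
| 95% | 23.75 | 23.75/32.45 = 73% | 1.25/22.55 = 6% | 0.67 |

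FAST women are the majority of achievers when m exceeds 30s/25: 13% at s = 10.9%, 35% at s = 29% and 60% at s = 50%. At s = 50% and m = 50% the share is 12.5/27.5 = 45%, and phi is 0.

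**What a pooled test would do, if one were made.** Simulation with 25 FAST and 30 SLOW women and a normal marker that differs by 0.8 SD between the groups but is unrelated to 6-month success within either. The test is a two-sided 5% Wilcoxon; the 0.8 SD is an assumption with no source in the documents.

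| m | s | Pooled test significant |
|---|---|---|
| 50% | 29% | 9% |
| 63.8% | 29% | 16% |
| 83% | 29% | 31% |
| 95% | 29% | 44% |
| 50% | 50% | 5% |

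Stratified by week-9 group, the rate stays at 5% to 6% for s = 29% and m = 50%, 83% and 95%. With a 0.5 SD shift, the pooled rate at m = 83% and s = 29% is about 15%.

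**Hypothesis 3.** This needs only the order of events. Baseline is measured, eight weeks of BWL follow, the split is made, and only then does Contrave start, in every SLOW woman. To learn who benefits from earlier drug treatment, the trial would need women who started it earlier, or comparable slow responders without it. It has neither.

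**The case against.** Objective 4.3.2 is exploratory and sets out to describe, not to test. Section 13.2 lists its groups already split by arm. The pooled description is also a legitimate question: who succeeds under the whole adaptive programme? A marker that acts through early response is a true predictor of that success, so the rejection rates above are not simple false positives. All of this stands, and it is why the pooled table may stay if it is labelled.

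A reader might infer three stronger things that the documents do not support.

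- *That a marker of success in SLOW women would be hidden.* It would not. Objective 4.2.2 and the SLOW-only logistic model look for it directly. With a 1.0 SD effect (assumed) and 29% success, a SLOW-only Wilcoxon test has about 60% power, against 13% to 25% for the pooled one.
- *That the pooled contrast is little more than the week-9 split again.* At 29% SLOW success, phi runs from 0.21 to 0.67 over the assumed maintenance range, and it can reach 0 if SLOW success is higher. The overlap is partial.
- *That 4.3.2 claims to show who benefits from the drug.* It makes no such claim. That language is in Hypothesis 3, is hedged, and attaches to the 2-month split.

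It is also fair to say that reporting by group does not recover drug benefit. Every SLOW woman is assigned Contrave, so the within-SLOW comparison is prognostic too. That limit comes from the single-arm design.

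**Conclusion.** The point holds as a minor one. The second half of 4.3.2 combines two groups with different treatment after week 9 and different distances to the 5% threshold. At the planned 29% SLOW success, FAST women would be about 59% to 73% of achievers, given an assumed 50% to 95% maintenance. The share depends on both rates and can fall below half. The size of any distortion is equally uncertain: from none, when both rates are 50%, to substantial, when maintenance is high and the marker shift is large.

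The last clause of Hypothesis 3 goes beyond what the design can show, whatever the rates turn out to be.

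The primary endpoint, sample size and stopping rule are unaffected.

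**What to change.** 1. In 4.3.2 and 13.2, report the 6-month achiever comparison by week-9 group: maintained versus not within FAST, reached versus not within SLOW. If one overall test is made, use a Wilcoxon test stratified by week-9 group (van Elteren) or a logistic model with a group term.
2. Label any pooled table as describing success under the whole adaptive programme.
3. In Hypothesis 3, change the last clause to *predictors of slow early response to BWL*. State that neither this comparison nor the within-SLOW one separates drug benefit from prognosis.

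The cost is a few sentences and no new data. The downside is an imprecise within-FAST comparison: 25 × (1 − m) gives about 1 to 13 non-maintainers over the assumed range, so it should be descriptive.

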
The ability of a diet and behavioral interventions to promote a more favorable microbiome profile, a lower BMI, and reduced levels of inflammatory cytokines, may help explain why vegetarian diets, and particularly vegan diets, seem to be protective against cancer growth in general and PC in particular. Our study, through its focus on inflammatory biomarkers, analysis of fecal microbiota, and traditional metabolic endpoints such as weight loss, adiposity, insulin resistance and hyperlipidemia, will help elucidate the complex interplay between metabolic disorders and inflammation in breast cancer survivors. Perhaps more importantly, we are confident that our study will offer breast cancer survivors a low-risk strategy to weight management, with tremendous potential for near-term impact on their quality of life and health outcomes. We will also assess certain genotypes to determine whether the effect of an adaptive weight loss intervention on biomarkers is greater in the patients who have a particular genotype (e.g. AA-SOD2). The potential increase in antioxidants in the adaptive weight loss intervention may enable certain patients with certain genotypes to gain greater benefit from the diet than others.

Our research will address a major gap in the literature that could potentially improve quality of life and cancer and non-cancer outcomes for obese breast cancer patients. While many studies have explored various interventions for weight loss in cancer survivors, to our knowledge none have explored the influence of weight loss pharmacotherapy in breast cancer survivors. Additionally, these medications have not been studied in the setting of use of hormonal therapy, such as tamoxifen or an aromatase inhibitor. The data will be used not only to assess the impact of weight loss and biomarker modulation but also to design definitive studies available to all overweight and obese women with breast cancer whom struggle to achieve clinically significant weight loss despite lifestyle intervention.

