7.4 Measurements

7.4.1 Weight: will be measured at each in-person visit, at approximately the same time of day. The weights are obtained at baseline, week 9 and at the end of study. The ideal weight measurement should be obtained within 7 days of completing the 8 weeks and 6 months behavioral intervention. However, to accommodate participants who may not be able to meet within this window, the weight measurement can be obtained within 14 days of these time points. Weight in light indoor clothes without shoes will be recorded by any trained, certified staff using a high-quality digital scale in any of our Johns Hopkins Medical Institute (JHMI) clinics. Duplicate measurements will be made to ensure accuracy. Weight will be measured in pounds for ease of interpretation by the participants and subsequently converted to kilograms for data analysis. Scales will be calibrated per the Sidney Kimmel Comprehensive Cancer Center's (SKCCC) standards. The engineering department or study staff will perform quarterly calibration checks by using standard weights. The weight at SV will be used to determine eligibility. Measurements will be repeated once, if difference between the two measurements is more than 0.1 kg, measurement will be repeated until difference between two measurements is less than 0.1 kg.

7.4.2 Height: to the nearest 0.1 cm will be measured once at any of our JHMI clinics. The participant stands shoeless on a firm, level surface, with her head in the horizontal (Frankfort) plane. Measurements will be repeated once, if difference between the two measurements is more than 1 cm, measurement will be repeated until difference between two measurements is less than 1 cm.

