9. CORRELATIVE STUDIES

9.1 Blood Samples

9.1.1 Collection

Approximately 15 mL (3 tubes) of blood will be collected at each time point (a standard 5 mL tube for lipid panel and Hba1c, one 10 mL red/gray research tubes). An additional 8 mL will be collected at the initial blood draw to include a 5mL red top tube for pregnancy test and 3 mL purple EDTA tube are collected for research once only. If blood samples are missed or unable to be obtained at any time point, this will not be considered a deviation and will not affect participant enrollment or continuation on the study. We will test glucose, insulin, lipid profiles (total cholesterol, HDL, LDL, and triglycerides), leptin and adiponectin, several fasting biomarkers, and various genotypes (e.g. MnSOD). The samples will be processed by either the central lab or local laboratories (See Lab Manual). In the event that blood cannot be collected, the subject may still take part in the other portions of the study.

	Baseline	2 months	6 months
Standard 5 mL gold tube (lipid panel, Hba1c)	X	X	X

Pregnancy test 5 mL red tube (if indicated)	X		
Purple 3 mL tube	X		
Red/gray 10 mL tube	X	X	X

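### Exploratory objective 4.3.3 is worded as a comparison of proportions by MnSOD genotype, with biomarker improvement undefined, although the outcomes are continuous; a continuous analysis would use about 55 women better

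*Combined protocol and SAP*

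**What the plan says.** Section 4.3.3 sets two genotype aims. The first is descriptive: "To assess prevalence of AA genotype of MnSOD in breast cancer survivors with excess weight". The second asks whether "a greater proportion of women with the AA genotype achieve ≥5% weight loss and improvement in biomarkers at 6 months". No section defines improvement in a biomarker, by direction, by size or by marker. The comparison group is given only as the women who do not, which can mean non-AA women or women who do not reach 5%.

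Two nearby statements use the language of size. Section 1 says that genotypes will be assessed to "determine whether the effect of an adaptive weight loss intervention on biomarkers is greater in the patients who have a particular genotype". Section 4.3.4 asks whether AA women given Contrave "have greater weight loss compared to women who do not receive Contrave".

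The underlying data are continuous. Section 7.4.1 states: "Weight will be measured in pounds for ease of interpretation by the participants and subsequently converted to kilograms for data analysis". Section 9.1.1 states: "We will test glucose, insulin, lipid profiles (total cholesterol, HDL, LDL, and triglycerides), leptin and adiponectin". On sample size, Section 13.1 says: "We anticipate 55% of 55 subjects enrolled will be in the SLOW-BWL group".

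Section 13.2 lists rank-sum and signed-rank tests, t-tests and mixed models for outcomes, and logistic regression for reaching 5%. It does not name genotype as a grouping in any of them.

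**The concern.** An analyst who follows 4.3.3 as worded would reduce 6-month weight change to a yes/no at 5% and each biomarker change to improved or not, then compare proportions between genotypes. A woman who loses 4.9% then counts the same as one who gains weight, and a trivial fall in leptin counts the same as a large one. The biomarker half cannot be computed at all until improvement is defined, and a definition chosen after the data are seen would be open to selection.

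The AA group may be small: 15-35% of 55 is about 8 to 19 women (an assumed range). The objective exists to inform later work, and an estimated difference with a confidence interval serves that better than two proportions from so few women. The 5% threshold is the primary endpoint's threshold. The plan does not say why a genotype association should be measured on it.

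**Working it through.** **The plan's own figure.** The plan states no power, effect size or SD for any genotype comparison. Its only power statement is for the primary endpoint. The two-stage rule in Section 13.1 (continue if more than 1 of 15, reject if at least 7 of 30) reproduces exactly: power 80.06% at a true rate of 29%, type I error 3.78% at 10.9%. It says nothing about genotype.

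**Inputs.** From the documents: N = 55. Assumed, because the documents are silent: AA share 15%, 25% or 35% (8 v 47, 14 v 41, 19 v 36); a normally distributed outcome with the same SD in both groups; a difference of d SD; half of all women reaching the cut; complete data; two-sided 5% level.

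**Continuous analysis.** Two-sample t-test, non-centrality d × √(n1·n2/(n1+n2)), with n1 + n2 − 2 = 53 degrees of freedom. For 14 v 41 and d = 0.8: 0.8 × √(574/55) = 2.584, which gives power 71.8%.

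**Same data after the cut.** Choose c so that [n1·Φ(c+d) + n2·Φ(c)]/55 = 0.5. For 14 v 41 and d = 0.8 the two proportions are 72.7% and 42.2%. Summing the two binomial distributions over all tables that the uncorrected chi-square test rejects gives power 51.2%. The loss is 71.8 − 51.2 = 20.6 points.

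**Across the assumptions** (t-test power / chi-square power, %, then loss in points):

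| AA v non-AA | 0.3 SD | 0.5 SD | 0.6 SD | 0.8 SD | 1.0 SD |
|---|---|---|---|---|---|
| 8 v 47 | 12.0 / 8.9, 3.1 | 25.0 / 16.5, 8.5 | 33.8 / 21.7, 12.1 | 53.7 / 34.4, 19.4 | 72.8 / 48.8, 24.0 |
| 14 v 41 | 15.8 / 11.6, 4.2 | 35.4 / 23.9, 11.5 | 47.7 / 32.2, 15.5 | 71.8 / 51.2, 20.6 | 88.7 / 69.6, 19.1 |
| 19 v 36 | 18.0 / 13.2, 4.8 | 41.0 / 28.3, 12.7 | 54.7 / 38.2, 16.5 | 79.1 / 59.7, 19.4 | 93.3 / 78.4, 14.9 |

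Losses are taken before rounding.

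**Choice of test for the proportions.** With no true difference, chi-square rejects 4.8-4.9% of the time in these three splits. Fisher's exact test rejects 2.4% (8 v 47), 2.9% (14 v 41) and 4.6% (19 v 36). Against Fisher the loss at 0.8 SD is 30.2, 29.0 and 20.3 points, but part of that comes from Fisher's conservatism and not from the cut. Chi-square is the fairer yardstick.

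**Position of the cut.** For 14 v 41 and 0.8 SD, an overall success rate of 46% (the POWER-remote result, Section 5.6) gives a loss of 18.5 points. A rate of 29% (the target in Section 13.1) gives 14.3.

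**Wider grid.** With AA 10-50%, success rates 29-61% and d from 0.3 to 1.2, a normal approximation gives losses from about 1 to 49 points. The cut loses power in every one of the 140 settings.

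**Information kept.** The large-sample efficiency of a cut at rate p is φ(z_p)²/[p(1−p)]: 0.637 at 50% and 0.569 at 29%.

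**The case against.** The strongest reply is that little hangs on this. The objective is exploratory, with no power claim, alpha or decision attached. The 5% threshold matches the primary endpoint, and Section 5.1 links loss of at least 5% to favourable changes in insulin and leptin. Section 13.2 already offers t-tests, rank-sum tests and mixed models, and Section 13.1 lists biomarker values as endpoints, so a continuous genotype analysis is possible under the present text. All of this stands, and it limits the point to a cheap improvement.

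Three stronger readings are tempting, and the documents support none of them.

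- A reader might infer that the plan commits to a binary genotype test. It does not: Section 13.2 assigns genotype no test. The wording of 4.3.3 points that way, and nothing corrects it.
- A reader might infer one fixed, large power loss, of 30 points or more. Such figures need Fisher's test or a large effect with few AA women, and the inputs are not in the plan.
- A reader might infer that the cut throws away most of the information. A cut at the median keeps about 64%.

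Nor is the cut the main reason why a small genotype effect would be missed. At 0.3 SD the t-test itself has only 12-18% power with 55 women.

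Missing data are a genuine counter-argument. Section 13.4 counts Contrave-treated women who drop out as failures, which keeps them in the denominator; a continuous outcome has no such default. Section 10.2.6 cites 42-50% attrition in the phase III trials, and Section 9.1.1 allows for missed blood: "If blood samples are missed or unable to be obtained at any time point, this will not be considered a deviation". If 30% were missing (an assumption), 14 v 41 becomes about 10 v 29 and t-test power at 0.8 SD falls from 72% to 57%. Counting dropouts as failures is not free either: if dropout is unrelated to genotype, it shrinks the difference in proportions. The rule in 13.4 also covers only SLOW-BWL women who received Contrave, while 4.3.3 is not limited to them.

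**Conclusion.** The point holds as a minor improvement. Objective 4.3.3 is worded as a comparison of proportions, one of its two outcomes is undefined, and its comparator is ambiguous. The measures beneath it are continuous, and the plan's own question is about size. On the assumptions shown (AA 15-35%, normal data, 55 complete women, half reaching the cut), the proportion analysis gives up about 3-5 points of power at 0.3 SD, 9-13 at 0.5 SD and 12-24 at 0.6-1.0 SD against an uncorrected chi-square test. These figures are conditional. The documents fix none of AA prevalence, SD or effect size, and the mix of FAST-BWL and SLOW-BWL women on different treatment makes a single normal distribution a simplification. The direction of the loss does not depend on the choice within the grid; its size does.

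**What to change.** Change the wording of 4.3.3 and add a genotype paragraph to 13.2:

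- State the comparison as AA versus non-AA women.
- Weight: linear regression of 6-month percent weight change from baseline on genotype.
- Biomarkers: linear regression of each 6-month value on genotype and its own baseline value, log-transformed or checked with a rank-based analysis where skewed. This removes the need to define improvement as a yes/no.
- Report differences with 95% confidence intervals, and keep the proportion reaching 5% by genotype as a description.
- State that women without 6-month data are handled by the multiple imputation already planned in 13.2.

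The cost is text only, with no new data or visits. There are two small downsides. Women without 6-month data must be imputed instead of counted as failures, and the main result is no longer a responder rate, although that rate is still reported.
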